## 5.2 Exclusion Criteria

Subjects are excluded from participation in the trial if any of the following criteria apply:

1.	Subjects who, in the opinion of the investigator, medical monitor, or sponsor, should not participate in the trial.
2.	Subjects who, in the judgment of the investigator, experienced poor tolerability to the IMP during the double-blind trial or whose safety assessments resulted in new concerns that would suggest that the subject may not be appropriate for 57 weeks of treatment with CVL-865 in an extension trial.
3.	Subjects who experienced status epilepticus during Trial CVL-865-SZ-001.
4.	Subjects who have demonstrated substantial noncompliance to trial procedures in Trial CVL-865-SZ-001, based on the investigator's judgement, would not be eligible for this trial. The medical monitor should be contacted if the investigator is unsure of a subject's eligibility.
5.	Subjects who answer "yes" on the C-SSRS Suicidal Ideation Item 4 or Item 5 (Active Suicidal Ideation with Some Intent to Act, Without Specific Plan, or Active Suicidal Ideation with Specific Plan and Intent), OR Subjects who answer "yes" on any of the 5 C-SSRS Suicidal Behavior Items (actual attempt, interrupted attempt, aborted attempt, preparatory acts, or behavior), OR Subjects who, in the opinion of the investigator, present a serious risk of suicide.
6.	Subjects with any of the following abnormalities in clinical laboratory tests at Visit 1, as assessed by the central laboratory and confirmed by a single repeat measurement, if deemed necessary: 

• Females: Hemoglobin <10 g/dL; Males: hemoglobin <11 g/dL

• White blood cell (WBC) count <3.0 × 10^9/L

• Neutrophil count <2.0 × 10^9/L

• Platelet count <150 × 10^9/L

7.	Subjects who would be likely to require the use of prohibited concomitant medications during the trial (as listed in Table 6 ).
8.	Female subjects who have a positive pregnancy test result.

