#### **9.4.1 Safety Analyses**

The safety analysis will be conducted on the Safety Set. The primary safety analysis is the frequency and severity of AEs during the Treatment Period. All AEs will be coded according to MedDRA preferred term. The incidence of treatment-emergent AEs (TEAEs) will include the following summaries:

- TEAEs by severity
- Drug-related TEAEs
- TEAEs with an outcome of death
- Serious TEAEs
- Discontinuations due to TEAEs

- TEAEs potentially related to abuse as assessed through the active monitoring of adverse events related to potential abuse and adverse events involving MHI

A TEAE is defined as an AE that started after the first dose of IMP in the open-label trial or a previously reported AE that increased in intensity, became serious, trial drug-related, or resulted in death, discontinuation, interruption, or reduction of IMP after the first dose of IMP in the open-label trial.

Other safety endpoints, including laboratory assessments, vital sign measurements, ECGs, medication withdrawal symptoms assessed by the mCIWA-B total scores at the scheduled visits and suicidality monitored during the trial using C-SSRS, will be summarized with descriptive statistics. Baseline is defined as the last assessment prior to the initiation of IMP in CVL-865-SZ-002. Additional presentations may be conducted evaluating changes from the original trial baseline. These analyses will be detailed in the statistical analysis plan.

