3.2.1.2. Pre-Treatment Adverse Event

Any recorded Adverse Event that occurs after obtaining informed consent but prior to the start of IMP.

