3.2.1.3. Treatment-emergent Adverse Event (TEAE)

Any event reported on the CRF that occurs on or after the initiation of IMP through the last follow up contact is considered treatment emergent. Additionally, it is assumed that an AE which was reported to have started on Day 1 without an associated onset time is assumed to be treatment emergent.

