4.1.3. Study Day 1 (Extension)

Day 1 is the day IMP is first initiated in CVL-865-SZ-002. The extension Day 1 will be referred to as 'Day 1' throughout the document.

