5. STATISTICAL ANALYSIS METHODS

5.1. General Considerations

Descriptive statistical methods will be used to summarize the data from this trial. Unless stated otherwise, the term “descriptive statistics” refers to number of subjects (N), number of observations (n), arithmetic mean, median, standard deviation (SD), first quartile (Q1), third quartile (Q3), minimum, and maximum for continuous data, and frequencies and percentages for categorical data. Certain figure presentations will include the standard error of the mean (SE). The term “treatment group” refers to treatment assignment in Trial CVL-865-SZ-001: Placebo, 7.5 mg BID CVL-865, 25 mg BID CVL-865 and assignment in Trial CVL-865-SZ-002: 25 mg BID CVL-865. All data collected from subjects who sign the informed consent form, including screen failures, will be included in data listings. Unless otherwise noted, the data listings will be sorted first by treatment, subject number and then by date within each subject number.

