5.8. Exposure to Treatment

The number of subjects who received IMP, treatment compliance, cumulative exposure to IMP (Double-Blind + Extension), days on IMP (Double-Blind and Extension), prematurely discontinued, and reason for IMP discontinuation will be summarized.

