5.12.1. Adverse Events

Adverse events will be mapped to a Medical Dictionary for Regulatory Activities (MedDRA) version 27.1 or higher PT and SOC. If a subject experiences multiple events that map to a single PT, the greatest intensity and strongest investigator assessment of relation to IMP will be assigned to the PT for the appropriate summaries. Events with missing intensity or relationship will be classified as outlined in [Section 4.1.21](#). Summaries of TEAEs will include any AEs reported beginning with the initiation of study drug on Day 1 through last follow up contact. The occurrence of TEAEs will be summarized by PTs, SOCs, and intensity. Separate summaries of treatment-emergent serious adverse events (TESAEs), TEAEs related to IMP, TEAEs leading to death, AESIs (including those potentially related to abuse as assessed through the active monitoring of adverse events related to potential abuse and AEs involving medication handling

irregularities), AESIs not leading to discontinuation of IMP, TEAEs leading to the discontinuation if IMP and events leading to discontinuation of study will be generated respectively. A presentation of AEs by dose at event onset will be prepared. All adverse events reported will be listed for individual subjects showing both verbatim and PTs. All adverse events that occurred prior to the initiation of study will be excluded from the tables but will be included in the listings.

Missing onset dates will be imputed as previously outlined in [Section 4.1.22](#) as required to determine TEAEs.

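### Every TEAE table starts at extension Day 1 and so mixes first, escalated and continued CVL-865 exposure; no planned AE table starts at the first CVL-865 dose

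*SAP*

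**What the plan says.** SAP 5.12.1 sets the window for all TEAE tables: "Summaries of TEAEs will include any AEs reported beginning with the initiation of study drug on Day 1 through last follow up contact". SAP 3.2.1.3 gives the definition, "Any event reported on the CRF that occurs on or after the initiation of IMP through the last follow up contact is considered treatment emergent", and SAP 4.1.3 fixes the anchor: "Day 1 is the day IMP is first initiated in CVL-865-SZ-002".

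Protocol 9.4.1 also counts from the first open-label dose. It adds "a previously reported AE that increased in intensity, became serious, trial drug-related" and certain fatal or dosing consequences; the SAP definition does not carry that addition.

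SAP 5.1 defines treatment group as "treatment assignment in Trial CVL-865-SZ-001: Placebo, 7.5 mg BID CVL-865, 25 mg BID CVL-865 and assignment in Trial CVL-865-SZ-002: 25 mg BID CVL-865". SAP 5.12.1 does not say which of these groups form the columns of the AE tables. It does plan one display of AEs by dose at onset.

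Protocol 4.1 and Table 4 titrate former placebo and former 7.5 mg subjects upward after extension Day 1 and keep former 25 mg subjects on their dose. Protocol 5.1 admits only subjects who completed SZ-001 treatment. Criterion 2 of Protocol 5.2 excludes those who, in the investigator's judgment, "experienced poor tolerability to the IMP during the double-blind trial".

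Other parts of the SAP reach back to SZ-001: exposure (5.8), CGI-S (5.11.2), laboratory values (5.12.4), vital signs (5.12.5), ECGs (5.12.6) and the C-SSRS comparison (5.12.9). No AE table does.

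**The concern.** The primary objective is long-term safety and tolerability, and the first-listed primary endpoint covers the timing of TEAEs as well as their frequency. The AE window is the same on the calendar for everyone but not in drug history. On its first day one group is drug-naive, one moves to dose levels it has not had, and one carries on unchanged. Completing SZ-001 and passing the tolerability criterion selects on CVL-865 tolerability only in the former active arms, because former placebo subjects had not yet taken the drug.

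A pooled extension incidence is therefore an average over different exposure histories. If the tables are split by SZ-001 arm, a higher figure in the former placebo column may only show that first exposure fell inside the window. An AE that began on CVL-865 in SZ-001 and persists unchanged is in no extension TEAE table under either definition.

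**Working it through.** **1. Window length.** The plan's own figures reproduce: 2 + 52 + 3 = 57 weeks of treatment, + 4 = 61 weeks. By study day: (379 − 15)/7 = 52, (400 − 379)/7 = 3, (428 − 400)/7 = 4. The window is equal for all arms.

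**2. Drug history at the start of the window.** Protocol 2.2 calls SZ-001 a 13-week trial. The dosing time up to its Visit 4 is not given, so 13 weeks is used as an upper bound.

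| SZ-001 arm | CVL-865 before extension Day 1 | Titration, weeks 1 and 2 | New inside the window |
|---|---|---|---|
| Placebo | none | 5, then 12.5 mg BID | all CVL-865 exposure |
| 7.5 mg BID | up to 13 weeks | 12.5, then 17.5 mg BID | every level above 7.5 mg BID |
| 25 mg BID | up to 13 weeks | 25, then 25 mg BID | no higher level |

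For a former active subject who completes treatment, the share of time on CVL-865 before counting starts is at most 13/(13 + 57) = 18.6%, and it is the earliest part.

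**3. Lower bound, with no assumption on rates.** Take the same former active subjects and the same end of follow-up. Moving the start back to the first CVL-865 dose can only keep or raise the number with at least one AE. For former placebo subjects the two starts coincide. So extension-only incidence is at or below cumulative incidence since first CVL-865 dose. This holds for the proportion of subjects, not for a rate per unit of exposure time.

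**4. Pooled figure against the drug-naive figure.** Let s be the former placebo share and r the risk in pre-exposed subjects, relative to naive subjects, inside the window. Then pooled/naive = s + (1 − s)r. The documents give neither s nor r, so both are assumed.

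| s | r = 0.25 | r = 0.5 | r = 0.75 | r = 1 | r = 1.25 |
|---|---|---|---|---|---|
| 1/4 | 0.44 | 0.63 | 0.81 | 1.00 | 1.19 |
| 1/3 | 0.50 | 0.67 | 0.83 | 1.00 | 1.17 |
| 1/2 | 0.63 | 0.75 | 0.88 | 1.00 | 1.13 |

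With s = 1/3 and an assumed naive incidence of 20%, the pooled figure is 10.0%, 13.3%, 16.7%, 20.0% and 23.3% across the row. If former 7.5 mg subjects react to escalation like naive subjects and only the 25 mg arm has r = 0.25, the ratio is (1 + 1 + 0.25)/3 = 0.75, giving 15.0%.

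**5. Rare first-exposure events.** With equal arms, about 120/3 = 40 subjects are seen from first exposure in the extension. For an event of 2% at first exposure, the chance of at least one case is 1 − 0.98^40 = 55%. If all 120 were seen from their first CVL-865 dose it would be 1 − 0.98^120 = 91%. The second figure ignores the selection of completers and is therefore optimistic.

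**6. Display by dose at onset, read against Table 4.** At 5 mg BID it merges former placebo subjects' first week with taper weeks. 12.5 mg BID occurs only in titration but merges two arms. 17.5 mg BID merges titration, reduced-dose maintenance and taper. 25 mg BID merges all arms.

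**The case against.** The protocol itself anchors TEAEs to the first open-label dose, there is no hypothesis, and no between-arm AE comparison is planned. Presentations against the original baseline are optional in Protocol 9.4.1. All of that stands: this is a gap in presentation, not an error against the protocol.

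The treatment-group definition in SAP 5.1 may mean that by-arm columns are already intended. If so, the former placebo column would isolate first exposure, and the first part of the fix only writes that down. The display by dose at onset also helps, but only in part, as step 6 shows.

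SZ-001 is the placebo-controlled trial in which the former active arms had their first exposure. A table built from rollover subjects cannot replace it: those who stopped early in SZ-001 are absent. This stands and must be stated on the table.

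Three stronger readings are tempting and not supported:

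- A reader might infer that pooling necessarily dilutes AE incidence. That requires r < 1. Early onset is plausible for a drug acting at the benzodiazepine site, but the documents give no AE rates, onset pattern or allocation ratio.
- A reader might infer from SAP 3.2.1.2, "Any recorded Adverse Event that occurs after obtaining informed consent but prior to the start of IMP", that on-drug events between consent and extension dosing are lost. Consent, Visit 1 and SZ-001 Visit 4 fall on one day, IMP taken after consent counts as extension IMP, and Day 1 events without an onset time are treated as emergent. The gap is nearly empty.
- A reader might infer that no exposure measure matches the AE window. SAP 4.1.8 defines extension-only days on IMP. What remains is narrower: the combined measure in SAP 4.1.9 runs from double-blind Day 1, and Protocol 6 includes placebo in IMP, so as written it counts placebo days for the former placebo arm.

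**Conclusion.** The point holds as a cheap improvement. The extension Day 1 anchor follows the protocol, but the resulting tables cannot separate first, escalated and continued exposure, and nothing in SAP 5.12.1 compensates fully. The contrast is sharpest between former placebo and former 25 mg subjects; the 7.5 mg arm lies between them.

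Two conclusions need no assumption about AE rates: extension-only incidence is a lower bound for former active subjects, and unchanged persisting AEs from SZ-001 go uncounted. The unobserved share of drug time is at most 18.6%, taking 13 weeks as the ceiling on prior dosing. The 0.50 to 0.83 ratio is an illustration for equal arms and r between 0.25 and 0.75. The pooled figure is not below the naive rate if r is 1 or more.

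**What to change.** Keep the TEAE definition and amend SAP 5.12.1:

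1. State that the TEAE, related, serious and discontinuation tables are shown by SZ-001 arm as well as pooled. Add a footnote giving each arm's CVL-865 exposure before extension Day 1.
2. Add a supplementary overall table and SOC/PT table of AEs with onset from the first CVL-865 dose: SZ-001 Day 1 for the two former active arms, extension Day 1 for former placebo. Show CVL-865 exposure time over the same period, with placebo days excluded. Label it as covering SZ-001 completers who rolled over, and as not estimating early discontinuation.
3. Add a count of subjects with an AE that began on CVL-865 in SZ-001 and was ongoing at extension Day 1.

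Separately, reconcile the SAP definition with the protocol's rule for worsening AEs; its absence mainly affects former active subjects.

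The cost is SAP wording, two or three extra tables, and merging SZ-001 AE records for the same subjects. SZ-001 baseline and exposure data are already used. The cumulative figures will look no better, and probably less favourable, than the extension-only ones. No protocol amendment, visits or subjects are needed.

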#### **Number of Subjects:**

The trial population will be derived from eligible subjects from the double-blind, proof-of-concept Trial CVL-865-SZ-001. Of the approximately 150 subjects to be enrolled in Trial CVL-865-SZ-001, approximately 120 are expected to complete the trial and be eligible for enrollment in Trial CVL-865-SZ-002.

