1.2. Sample Size Considerations

The sample size is not based on statistical power considerations. The trial population will be derived from eligible subjects from the double-blind, proof-of-concept Trial CVL-865-SZ-001. Approximately 120 subjects are expected to complete Trial CVL-865-SZ-001 and be eligible for enrollment in Trial CVL-865-SZ-002.

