5.3. Statistical Hypotheses

There is no statistical hypothesis for this open-label trial.

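### The TEAE tables are planned as crude subject percentages with no person-time or censoring-aware summary, so they may understate long-term risk by an amount that depends on dropout.

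*SAP*

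**What the plan says.** Protocol 9.4.1 defines the target of the safety analysis: "The primary safety analysis is the frequency and severity of AEs during the Treatment Period". The Treatment Period is up to 57 weeks (2 titration, 52 maintenance, 3 taper). The primary endpoint in SAP Section 2 covers the timing of TEAEs as well as their kind and frequency.

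SAP 5.12.1 gives the main output: "The occurrence of TEAEs will be summarized by PTs, SOCs, and intensity". It adds separate summaries for serious, related and fatal TEAEs, AESIs, and TEAEs leading to discontinuation, and a display by dose at onset. It counts TEAEs from the first dose in this trial through the last follow-up contact, which is about Week 61 for a completer.

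SAP 5.12.1 does not name the statistic. SAP 5.1 supplies it as "frequencies and percentages for categorical data", and SAP 9.3 makes the denominator a count of subjects. The Safety Set (SAP 5.2) is everyone with at least one dose, however long they stayed.

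Time on drug is tabulated under SAP 5.8: "days on IMP (Double-Blind and Extension), prematurely discontinued, and reason for IMP discontinuation will be summarized". It is not linked to adverse events anywhere.

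**The concern.** The trial exists to describe long-term safety and has no control arm, so these percentages will be read as its answer. Follow-up will not be equal. Under Protocol 7.3 and the footnotes to Table 3, a subject who stops early goes through the 3-week taper and 4-week follow-up, or has a final visit about 30 days after the last dose. Observation then ends, within roughly 7 weeks of the decision to stop. From that point the subject can contribute no event but still counts in full in the denominator.

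The effect is greatest for events that arise late. Protocol 2.2 reports multiple dosing for up to 4 weeks before this programme, and Protocol 2.3 names bone marrow suppression and falling blood counts as potential risks. Whether these arise late is not known, which is a reason to use a summary that does not depend on it.

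The SAP already makes this kind of adjustment elsewhere: SAP 3.1.1 divides seizure counts by the days with data. The primary safety outcome has no counterpart.

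**Working it through.** **The plan's own figures.** There is no power calculation to reproduce. SAP 5.3 says "There is no statistical hypothesis for this open-label trial" and SAP 1.2 says "The sample size is not based on statistical power considerations". The durations agree: 2 + 52 + 3 = 57 weeks; (400 − 1)/7 = 57.0 weeks to the end of taper; (428 − 1)/7 = 61.0 weeks to Visit 17. The expected size follows from Protocol 1.1: "Of the approximately 150 subjects to be enrolled in Trial CVL-865-SZ-001, approximately 120 are expected to complete the trial", that is 120/150 = 80%.

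**Inputs not in the documents.** Neither document gives a dropout rate or an event rate for this extension. Both are assumed below: dropout of 10%, 20% or 30% by Week 57, and a true risk of 10% over T = 57 weeks with everyone followed.

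**Model.** Let the event hazard be l and the dropout hazard c, both constant and independent of each other. With risk p and dropout proportion d, lT = −ln(1 − p) and cT = −ln(1 − d). The expected crude proportion is

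crude = l/(l + c) × [1 − exp(−(l + c)T)].

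For p = 0.10 and d = 0.20, lT = 0.1054 and cT = 0.2231. Then l/(l + c) = 0.1054/0.3285 = 0.321, and 1 − 0.9 × 0.8 = 0.28. The product is 0.0898, so 10% shows as 9.0%.

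**Effect of onset timing.** The same calculation was run with all the risk confined to the first 2 weeks (titration), and with all of it after Week 26.

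| Dropout by Week 57 | Constant hazard | First 2 weeks only | After Week 26 only |
|---|---|---|---|
| 10% | 9.5% | 10.0% | 9.3% |
| 20% | 9.0% | 10.0% | 8.5% |
| 30% | 8.4% | 9.9% | 7.7% |

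The true risk is 10% in every cell. With constant hazard, the relative shortfall is about 5%, 10% and 16%. For true risks from 2% to 50% the ratio of crude to true is 0.95 to 0.96, 0.90 to 0.91 and 0.84 to 0.86, so about 15% at 30% dropout is a fair summary. For onset after Week 26 the shortfall is about 7%, 15% and 23%.

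**Does a person-time rate recover the risk?** In a simulation of 2 million subjects at 20%, 30% and 50% dropout, the first-event rate was about 9.7 per 100 person-years each time. Converted by 1 − exp(−rate × T), it gave 10.0% each time. This holds under the constant hazard that was simulated.

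The illustration stops at Week 57, while TEAEs are counted to about Week 61. Subjects who stop treatment are also observed for some weeks afterwards, so dropout here means leaving follow-up, not stopping drug.

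**The case against.** Three stronger readings are tempting, and the documents do not support them.

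- **A reader might infer that every early dropout is counted as event-free.** That is not so. A subject with the event before leaving is counted, including one who leaves because of it, and counting continues through taper and follow-up. Only those who leave follow-up without that event matter.
- **A reader might infer that the incidence is definitely understated, and by a third or more.** Carrying the parent trial's 20% per 13 weeks forward gives 1 − 0.8^(57/13) = 62% dropout. A 10% risk would then show as 6.5% with constant hazard, or 5.0% if it arises only after Week 26. But the 20% is a planning figure that may include ineligibility, and this extension enrols only completers, excluding those with poor tolerability or substantial noncompliance (Protocol 5.1 and 5.2). It is not an estimate of dropout here.
- **A reader might infer that an arm with more dropout will look safer.** SAP 5.1 defines treatment group by both the parent-trial assignment and the extension dose. SAP 5.12.1 specifies no columns and no comparison between arms.

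The best case for the plan is that the trial is descriptive and the crude percentage correctly gives the proportion observed with an event. Neither document defines the target as the risk with everyone followed to Week 57. Other outputs also help. Blood counts are summarised by visit among those with data (SAP 5.12.4, 9.3), narratives for abuse-related terms record time to onset (Protocol 8.4.6.1), and days on study and on IMP are tabulated (SAP 5.7, 5.8).

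All of that stands, and it limits the point to a possible understatement of unknown size. It does not remove the gap. A reader cannot combine a separate table of days on IMP with a percentage to obtain a rate for serious TEAEs or any AESI class.

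**Conclusion.** The point holds in a limited form. The planned TEAE tables take no account of time at risk, in a trial whose primary objective is long-term safety. Crude percentages may therefore understate the risk under full follow-up. On assumed dropout of 10% to 30%, with constant hazards and dropout unrelated to event risk, the shortfall is about 5% to 15% relative. It is close to zero for titration-phase events and larger for late ones. The true size cannot be known from the documents, which state neither dropout nor onset timing for this extension. That the tables are crude percentages is inferred from SAP 5.1 and 9.3, since SAP 5.12.1 does not name the statistic. This is a cheap improvement; nothing in the crude tables is wrong as a description of what was observed.

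**What to change.** In SAP 5.12.1, keep the crude tables and add two outputs.

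1. For any TEAE, serious TEAEs, TEAEs leading to IMP discontinuation and each AESI class: subjects with a first event per 100 person-years at risk, with a 95% confidence interval. Count time from Day 1 to the first event or the last follow-up contact, so that it matches the TEAE window. Report overall and, if the tables are shown by parent-trial arm, by arm.
2. For serious TEAEs and hematologic AESIs: cumulative incidence at about Weeks 26 and 54, censored at last contact, with death as the competing event. Stopping IMP for another adverse event should not be a competing event, because TEAEs are still counted after IMP stops.

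Footnote that the rates assume a roughly constant hazard, and that both outputs assume dropout unrelated to event risk. For TEAEs leading to IMP discontinuation, also note that the weeks after the last dose carry no risk of that event.

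The cost is SAP wording and a few extra tables. The inputs are already collected: adverse event onset dates, first dose date and the dates of follow-up contact. No protocol change or new assessment is needed.
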